3.3 Rationale for Dose and Escalation Timing

In this study all subjects will initially be administered 1 mg/kg SBC-103 qow by IV infusion, see Section 1.5.1 for dose justification.

3.3.1 Decision for Continued Dosing after the First Dose in Each Subject

Due to the relatively limited experience with SBC-103 in humans (as of 30 April 2015), 24-hour in-patient safety monitoring following the first dose for each subject will be conducted in this study. The Sponsor and PI will review safety data from the first dose in each subject prior to continuation of dosing in that subject.

Page 38 of 104

ALEXION PHARMACEUTICALS, INC. PROPRIETARY AND CONFIDENTIAL: DO NOT COPY OR DISTRIBUTE WITHOUT PERMISSION FROM ALEXION

3.3.2 Decision for Dose Escalation Within a Subject after 12 Weeks of Treatment

Considering the potential for immunogenicity with a protein product, evaluation of the safety and tolerability following multiple rather than single doses prior to escalation is important (see Section 1.3). Therefore, the decision to escalate to 3 mg/kg will be made by the Sponsor and PI only after review of safety, tolerability and PD data from each subject after they have completed a minimum of 12 weeks of treatment. This data review will include HS data from CSF evaluation at 12 weeks and the HS data from serum and urine samples every 4 weeks, along with multiple dose safety and tolerability data.

3.3.3 Additional Dose Adjustment During the Study

Additional dose modifications (including reductions in dose) may be considered by the Sponsor after consultation with the PI, based on review of safety and tolerability data as well as biomarker and response to treatment data.

Dose modification of increasing the dose to 3 mg/kg can only occur after 12 weeks of treatment and review of data as described above.

Dose modification of decreasing the dose to 1 mg/kg or 0.3 mg/kg can occur for individual subjects at any point in the study to manage subject safety and/or response to treatment data. The independent SRC for the SBC-103 program will continue to provide oversight of subject safety through periodic reviews of safety data. Dose frequency (e.g., weekly) modifications may be considered by the Sponsor after consultation with the SRC and PI, based on a review of safety, tolerability, and response to treatment data.

During the study the SRC, Sponsor or PI may request a pause in dosing in individual, multiple or all subjects based on review of reported events and available data. Dosing will resume only after the review of data and agreement to do so by the SRC, Sponsor and PI.

3.4 Study Endpoints

3.4.1 Primary Endpoint

The primary endpoint of this study is safety and tolerability of SBC-103 in subjects with MPS IIIB. The safety assessments will include the following:

- Incidence of AEs, SAEs, and IARs.
- Changes from baseline in clinical laboratory tests (haematology, serum chemistry, and urinalysis) and CSF findings (cell counts, glucose, and protein).
- Changes from baseline in 12-lead ECGs.
- Changes in vital signs during and post-infusion, relative to pre-infusion values.
- Physical examination findings.
- Use of concomitant medications/therapies.

• Incidence of ADAs, including seroconversion rate, time to seroconversion, and ADA titre by time point, peak ADA titre, and ADA titre status (positive/negative), and the effect of ADAs on the safety of SBC-103, including the relationship between ADA-positive subjects and the incidence of IARs.

3.4.2 Secondary Endpoints

The secondary endpoints of this study are:

- PK profile of SBC-103 after single and multiple doses as measured by:
 - Serum maximum concentration (C_{max}).
 - Time to maximum concentration (T_{max}).
 - Area-under-the-concentration-time curve extrapolated to infinity (AUC_{∞}) .
 - Half-life $(T_{1/2})$.
 - Clearance (Cl).
 - Apparent volume of distribution at steady state (V_{ss}).
- Onset and magnitude of changes in levels of total HS in CSF, serum, and urine following dosing with SBC-103 administered IV.
- Change from the NGLU-CL01 study visit to baseline of the NGLU-CL01-T study (observational period) in CSF, serum, and urine HS in the absence of treatment.
- Changes from the NGLU-CL01 study visit to baseline of the NGLU-CL01-T study (observational period) in the following:
 - Clinical laboratory tests (haematology, serum chemistry, and urinalysis) and CSF findings (cell counts, glucose, and protein).
 - 12-lead ECGs.
 - Vital signs.
 - Physical examination.
 - Use of concomitant medications/therapies.
- Change in neurocognitive and developmental function during the NGLU-CL01-T study (on treatment), as determined by Vineland Adaptive Behavior Scales, Second Edition (Vineland-II).
- Change in neurocognitive and developmental function from the NGLU-CL01 study visit to baseline of the NGLU-CL01-T study (observational period), as determined by Vineland-II.
- Change in neurocognitive and developmental function during the NGLU-CL01-T study (on treatment) as determined by the subject's age-appropriate scores, the Bayley Scales of Infant and Toddler Development, Third Edition (BSID-III) or Kaufman Assessment Battery for Children, Second Edition (KABC-II), Bruininks-Oseretsky Test of Motor Proficiency, Second Edition, Brief Form (BOT-2 Brief Form), and Children's Communication Checklist, Second Edition (CCC-2).

- Changes in brain structure, as measured by the relative proportion of grey and white matter volume, and indices of microstructural integrity, as assessed by MRI of the brain during the NGLU-CL01-T study (on treatment).
- Changes in brain structure, as measured by the relative proportion of grey and white matter volume, and indices of microstructural integrity, as assessed by MRI of the brain, from the NGLU-CL01 study visit to baseline of the NGLU-CL01-T study (observational period).
- Changes in BBB integrity during the NGLU-CL01-T study (on treatment), as determined by CSF-AI.
- Changes in BBB integrity from the NGLU-CL01 study visit to baseline of the NGLU-CL01-T study (observational period), as determined by CSF-AI.

3.4.3 Exploratory Endpoints

Onset and magnitude of changes in biomarkers, SBC-103 concentration in CSF, MPS IIIB disease characteristics and symptoms, and QOL after administration of SBC-103 (on treatment):

- Biomarkers:
 - Change in NRE HS derivatives in CSF, serum, and urine.
 - Changes in serum ferritin and chitotriosidase.
 - Changes in CSF disease-related biomarkers including, but not limited to, hepatocyte growth factor, calbindin D, Tau, pTau, amyloid β, albumin, IgG, glutamic acid, and glycine.
 - Changes in glutamic acid and glycine in relation to plasma (carrier-mediated excitatory amino acids that are markers of transport function).
 - Changes in CSF IgG Index ([CSF/serum IgG ratio] / [CSF-AI]). CSF IgG Index is a measure of IgG synthesis within the CNS.
 - Changes in inflammatory markers in serum.
 - Changes in other blood or urine biomarkers of interest that are identified during the course of this study based on emerging data from the scientific literature or the Sponsor's MPS IIIB development program (if there is sufficient sample volume and if local regulations permit).
- Disease characteristics and symptoms, and QOL.
- Coarsening of facial features, as determined by Facial Dysmorphology Novel Analysis (FDNA).
- SBC-103 concentration in CSF.
- Changes in measures of sleep disorders or dysfunction, as assessed by the Children's Sleep Habits Questionnaire (CSHQ).

- Changes in measures of behaviour, as determined by the Sanfilippo Behavior Rating Scale (SBRS).
- Changes in subjective QoL measures, as determined by the Short Form Health Survey for Children (SF-10).
- Changes in measures of caregiver QoL, as determined by the Zarit Burden Interview (ZBI) 12-item short form.

Onset and magnitude of changes in biomarkers and MPS IIIB disease characteristics and symptoms from the NGLU-CL01 study visit to baseline of the NGLU-CL01-T study (observational period):

- Biomarkers:
 - Change in NRE HS derivatives in CSF, serum, and urine.
 - Changes in serum ferritin and chitotriosidase.
 - Changes in CSF disease-related biomarkers including, but not limited to, hepatocyte growth factor, calbindin D, Tau, pTau, amyloid β, albumin, IgG, glutamic acid, and glycine.
 - Changes in glutamic acid and glycine in relation to plasma (carrier-mediated excitatory amino acids that are markers of transport function).
 - Changes in inflammatory markers in serum.
- Disease characteristics and symptoms.
- Coarsening of facial features, as determined by FDNA.

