Serum, and where possible, urine, will be collected for analysis of MPS IIIB substrate (total HS) and other disease-related biomarkers including NRE HS derivatives. CSF will be collected via lumbar puncture for analysis of total HS and other disease-related biomarkers including NRE HS derivatives. All efforts will be made to obtain a blood sample to evaluate serum albumin and serum IgG at the same time as the CSF sample, as reflected in the SOA. The CSF-AI will be calculated as the CSF albumin (mg/mL)/serum albumin (g/L). IgG index will be calculated as the ([CSF/serum IgG ratio] / [CSF-AI]). Refer to Section 5.2.1.3 for details regarding the lumbar puncture.

A specific sample for biomarker analysis is being collected in this study; however, remaining blood and urine samples collected in this study may also be used to analyse additional biomarkers of potential clinical interest, if there is sufficient sample and where local regulations permit. As subjects with MPS IIIB may be incontinent, urine samples for routine assessments and biomarkers may not be able to be collected, but should be attempted whenever possible.

Due to the limitations on the volume of blood collection that is considered to be acceptable in young children with very small total circulating blood volumes; see Committee for Medicinal Products for Human Use and Paediatric Committee guidance (EMEA/536810/2008, adopted 25 June 2009), the blood laboratory tests will be ranked by tier. Per individual, the study-related blood loss should not exceed 3% of the total blood volume during a period of 4 weeks and should not exceed 1% at any single time. The total volume of blood is estimated at 80 to 90 mL/kg body weight; 3% corresponds to about 2.4 to 2.7 mL blood per kg body weight.

Tier 1 assessments (see Table 1) are considered mandatory and all efforts should be made to collect these samples in all subjects. Samples for the Tier 2 or Tier 3 assessments will be collected if permitted based on the blood or CSF volume threshold for a subject's weight, as well as the subject's clinical status. All tests will be performed by a qualified laboratory.

Clinical laboratory samples will be stored by the Sponsor or designee in a secure and controlled environment until analysis, and will be destroyed by the Sponsor or designee after all worldwide obligations have been met, or sooner if required by local regulations.

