Pregnancy Test (Urine) ⁴		X ^p											
Serum and Urine Heparan Sulphate (Total and NRE)				X ^p				X ^p					X ^P
Serum Ferritin and Chitotriosidase				X^P				X^P					X^P
Plasma Glutamic Acid and Glycine				X^P				X^P					X^P
Serum Biomarkers (Exploratory including IgG, inflammatory markers)				X ^P				X ^P					X ^P

Page 94 of 104

Assessments	Week 54	Week 56	Week 58	Week 60	Week 62	Week 64	Week 66	Week 68	Week 70	Week 72	Week 74	Week 76	Week 78
Visit Window (Days)	±5 days	±5 days	±5 days	±5 days	±5 days	±5 days	±5 days	±5 days	±5 days	±5 days	±5 days	±5 days	±5 days
Serum Pharmacokinetic Profile ⁵	aujs	uuys	aujo	uujo	aujo	uujo	aujo	uujo	auys	uujo		uujo	X
SBC-103 ADA ⁶		X ^P		X^{P}		X^{P}		X ^P		X ^P		X ^P	
General Anaesthesia/Sedation ⁷								X^{P}					X ^P
Lumbar Puncture ^{7,8}								X ^P					X ^P
Heparan Sulphate (Total and NRE) in CSF								X ^P					X ^P
Calbindin D, HGF, Tau, pTau, Amyloid β, Albumin, IgG in CSF								X ^p					X ^p
Glutamic Acids and Glycine in CSF								X ^P					X ^P
Routine Findings (Cell Counts, Glucose, Protein) in CSF ³								X ^p					X ^p
SBC-103 in CSF								X ^P					X ^P
SBC-103 Dosing	Х	Х	Х	Х	Х	Х	Х	Х	Х	Х	Х	Х	Х
Adverse Events ¹⁰						(CONTINUOU	JS					
Concomitant Medications ¹¹							CONTINUOU	JS					

	Week	Week	Week	Week	Week	Week	Week	Week	Week	Week	Week	Week	Week
Assessments	80	82	84	86	88	90	92	94	96	98	100	102	104
	±5	±5	±5	±5	±5	±5	±5	±5	±5	±5	±5	±5	±5
Visit Window (Days)	days	days	days	days	days	days	days	days	days	days	days	days	days
Physical Examination	\mathbf{X}^{P}		X ^P		X ^P		X ^P		X ^P		X ^P		X ^P
Height and Weight	X^{P}		X ^P		X ^P		X ^P		X ^P		X ^P		X ^P
Vital Signs ¹²	Х	Х	Х	Х	Х	Х	Х	Х	Х	Х	Х	Х	Х
12-lead ECG ¹													X ^P
FDNA													Х
Vineland-II, BSID-III, KABC-II, BOT-2 Brief Form, CSHQ, CCC-2, SBRS, ZBI, SF-10 ²													X ^P
Haematology, Serum Chemistry (including Coagulation), Urinalysis ³				X ^p				X ^p					X ^P
Serum albumin sample						X ^P							
Pregnancy Test (Urine)	X ^P		X ^P		X ^P		X ^P		X ^P		X ^P		X ^P
Serum and Urine Heparan Sulphate (Total and NRE)				X ^P		X ^P		X ^P					X ^P
Serum Ferritin and Chitotriosidase				X ^P				X ^P					X^{P}
Plasma Glutamic Acid and Glycine				X ^P				X ^P					X^{P}
Serum Biomarkers (Exploratory including IgG, inflammatory markers)				X ^P				X ^P					X ^P

Page 96 of 104

Assessments	Week 80	Week 82	Week 84	Week 86	Week 88	Week 90	Week 92	Week 94	Week 96	Week 98	Week 100	Week 102	Week 104

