Visit Window (Days)	±5 days	±5 days	±5 days	±5 days	±5 days	±5 days	±5 days	±5 days	±5 days	±5 days	±5 days	±5 days	±5 days
Serum Pharmacokinetic Profile ⁵			aujs	aujo	aujo	aujo	aujs	aujo		aujs	awy s		X
SBC-103 ADA ⁶	X^{P}		X ^P		X ^P		X ^P		X ^P		X ^P		X ^P
General Anaesthesia/Sedation ⁷						X ^P							X ^P
Lumbar Puncture ^{7,8}						X ^P							X ^P
Heparan Sulphate (Total and NRE) in CSF						X ^P							X ^P
Calbindin D, HGF, Tau, pTau, Amyloid β, Albumin, IgG in CSF						X ^p							X ^P
Glutamic Acids and Glycine in CSF						X ^p							X ^p
Routine Findings (Cell Counts, Glucose, Protein) in CSF ³						X ^p							X ^P
SBC-103 in CSF						X ^P							X ^P
Structural and Diffusion MRI ⁷													X ^P
SBC-103 Dosing	Х	Х	Х	Х	Х	Х	Х	Х	Х	Х	Х	Х	Х
Adverse Events ¹⁰							CONTINUOU	JS					
Concomitant Medications ¹¹							CONTINUOU	JS					

Assessments	Week 106	Week 108	Week 110	Week 112	Week 114	Week 116	Week 118	Week 120	Week 122	Week 124	Week 126	Week 128	Week 130	Week 132
1 1950551101105	100	100	110	112		110	110	120	122	121	120	120	100	102
	±5	±5	±5	±5	±5	±5	±5	±5	±5	±5	±5	±5	±5	±5
Visit Window (Days)	days	days	days	days										
Physical Examination		X ^P		X ^P		X^{P}		X ^P		X ^P		X ^P		X ^P
Height and Weight		X ^P		X ^P		X^{P}		X ^P		X^{P}		X ^P		X ^P
Vital Signs ¹²	Х	Х	Х	Х	Х	Х	Х	Х	Х	Х	Х	Х	Х	Х
12-lead ECG ¹													X ^P	
FDNA													Х	
Vineland-II, BSID-III, KABC-II, BOT-2 Brief Form, CSHQ, CCC-2, SBRS, ZBI, SF-10 ²													X ^p	
Haematology, Serum Chemistry (including Coagulation), Urinalysis ³				X ^p				X ^P					X ^p	
Pregnancy Test (Urine) ⁴		X ^P		X ^P										
Serum and Urine Heparan Sulphate (Total and NRE)				X^{P}				X^{P}					X ^p	
Serum Ferritin and Chitotriosidase				X^{P}				X^{P}					X ^p	
Plasma Glutamic Acid and Glycine				X^{P}				X^P					X^{P}	
Serum Biomarkers (Exploratory including IgG, inflammatory markers)				X ^P				X ^P					X ^P	
Serum Pharmacokinetic Profile ⁵													Х	
SBC-103 ADA ⁶		X ^P		X ^P		X^{P}		X ^P		X ^P		X ^P		X ^P

Page 98 of 104

Assessments	Week 106	Week 108	Week 110	Week 112	Week 114	Week 116	Week 118	Week 120	Week 122	Week 124	Week 126	Week 128	Week 130	Week 132
	±5	±5	±5	±5	±5	±5	±5	±5	±5	±5	±5	±5	±5	±5
Visit Window (Days)	days	days	days	days	days	days	days							
General Anaesthesia/Sedation ⁷								X^{P}					X^P	
Lumbar Puncture ^{7,8}								X ^P					\mathbf{X}^{P}	
Heparan Sulphate (Total and NRE) in CSF								X^{P}					X^{P}	

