Calbindin D, HGF, Tau, pTau, Amyloid β, Albumin, IgG in CSF								X ^p					X ^p	
Glutamic Acids and Glycine in CSF								X^{P}					X^P	
Routine Findings (Cell Counts, Glucose, Protein) in CSF ³								X ^P					X ^P	
SBC-103 in CSF								X ^P					X ^P	
SBC-103 Dosing	Х	Х	Х	Х	Х	Х	Х	Х	Х	Х	Х	Х	Х	Х
Adverse Events ¹⁰							CONTI	NUOUS						
Concomitant Medications ¹¹							CONTI	NUOUS						

Page 99 of 104

Assessments	Week 134	Week 136	Week 138	Week 140	Week 142	Week 144	Week 146	Week 148	Week 150	Week 152	Week 154	Week 156/ End of Treatment/ Early Termination	Week 160
	±5	± 5	±5	±5	± 5	± 5	± 5	± 5	± 5	±5	±5	±5	± 5
Visit Window (Days)	days	days	days	days	days	days	days	days	days	days	days	days	days
Physical Examination		X ^P		X ^P		X ^P		X ^P		X ^P		X ^P	
Height and Weight		X ^P		X ^P		X ^P		X ^P		X ^P		X ^P	
Vital Signs ¹²	Х	Х	Х	Х	Х	Х	Х	Х	Х	Х	Х	Х	
12-lead ECG ¹												X ^P	
FDNA												Х	
Vineland-II, BSID-III, KABC-II, BOT-2 Brief Form, CSHQ, CCC-2, SBRS, ZBI, SF-10 ²												X ^p	
Haematology, Serum Chemistry (including Coagulation), Urinalysis ³			X ^p				X ^p					X ^p	
Serum Albumin sample					Х								
Pregnancy Test (Urine) ⁴		X ^P		X ^P		X^P		X ^P		X ^P		X ^P	
Serum and Urine Heparan Sulphate (Total and NRE)			X^{P}		X^{P}		X^{P}					X^{p}	
Serum Ferritin and Chitotriosidase			X^{P}				X^{P}					X^{p}	
Plasma Glutamic Acid and Glycine			X^{P}				X^{P}					X^{P}	
Serum Biomarkers (Exploratory including IgG, inflammatory markers)			X ^P				X ^P					X ^p	
Serum Pharmacokinetic Profile ⁵												Х	

Page 100 of 104

Assessments	Week 134	Week 136	Week 138	Week 140	Week 142	Week 144	Week 146	Week 148	Week 150	Week 152	Week 154	Week 156/ End of Treatment/ Early Termination	Week 160
Visit Window (Days)	±5 days	±5 days	±5 days	±5 days	±5 days	±5 days	±5 days	±5 days	±5 days	±5 days	±5 days	±5 days	±5 days
SBC-103 ADA ⁶	uays	X ^P	uays	X ^P	uays	X ^P	uays	X ^P	uays	X ^P	uays	XP	uays
General Anaesthesia/Sedation ⁷					X ^P							X ^p	
Lumbar Puncture ^{7,8}					X ^P							X ^p	
Heparan Sulphate (Total and NRE) in CSF					X ^P							X ^p	
Calbindin D, HGF, Tau, pTau, Amyloid β, Albumin, IgG in CSF					X ^p							X ^p	
Glutamic Acids and Glycine in CSF					X ^P							X ^p	
Routine Findings (Cell Counts, Glucose, Protein) in CSF ³					X ^p							X ^p	
SBC-103 in CSF					X ^P							X ^P	
Structural and Diffusion MRI ⁷												X ^P	
Telephone call ⁹													Х
SBC-103 Dosing	Х	Х	Х	Х	Х	Х	Х	Х	Х	Х	Х	Х	
Adverse Events ¹⁰		CONTINUOUS											

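### At Weeks 90 and 142 the schedule takes CSF glutamic acid and glycine without same-visit plasma, and leaves out the serum IgG that Section 5.2.1 calls for

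*Protocol*

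**What the plan says.** Protocol Section 3.4.3 names two on-treatment exploratory measures that combine CSF with blood. One is "Changes in glutamic acid and glycine in relation to plasma (carrier-mediated excitatory amino acids that are markers of transport function". The other is the CSF IgG index, defined as the CSF/serum IgG ratio divided by the CSF/serum albumin index (CSF-AI).

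Section 5.2.1 gives the sampling instruction for the second: "All efforts will be made to obtain a blood sample to evaluate serum albumin and serum IgG at the same time as the CSF sample". It adds that the SOA reflects this. No text gives a matching instruction for plasma amino acids.

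Table 1 lists CSF-AI and the IgG index together as one Tier 1 CSF/serum entry, and Section 5.2.1 treats Tier 1 as mandatory. Serum IgG, and plasma glutamic acid and glycine, appear separately as Tier 2. Footnote b, attached to the index entry, asks only for serum albumin at each CSF time point. Section 5.2.1.3 and SOA footnote 8 likewise ask only for albumin.

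Four Appendix A rows matter here: "Glutamic Acids and Glycine in CSF", "Plasma Glutamic Acid and Glycine", "Serum Biomarkers (Exploratory including IgG, inflammatory markers" and the row headed "Serum albumin sample" (Weeks 80–104 block) or "Serum Albumin sample" (Weeks 134–160 block). SAP Appendix 9.1 reproduces the same schedule.

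**The concern.** A measure of CSF amino acids relative to plasma is most naturally read as using plasma and CSF from the same visit, and the IgG index needs serum IgG to go with the CSF IgG. If the blood is not drawn, the CSF result at that visit cannot be used for the derived measure without borrowing a value from another visit.

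The CSF comes from a lumbar puncture, under general anaesthesia or sedation, in cognitively impaired subjects. With at most 5 subjects and descriptive analysis only, an avoidable gap in the paired series is worth closing if it can be done cheaply.

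**Working it through.** The documents give no figure to reproduce. The check is a column-by-column reading of the six Appendix A blocks.

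**Step 1: CSF visits.** Lumbar puncture is marked at Day 0 and Weeks 12, 24, 36, 52, 68, 78, 90, 104, 120, 130, 142 and 156. That is 13 visits, 12 of them post-baseline.

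**Step 2: matching blood.** The plasma amino acid row and the serum row containing IgG are both marked at every one of these visits except Weeks 90 and 142.

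| Row | Weeks 80–104 | Weeks 134–160 |
|---|---|---|
| Lumbar puncture; CSF amino acids; CSF albumin and IgG | 90, 104 | 142, 156 |
| Plasma glutamic acid and glycine | 86, 94, 104 | 138, 146, 156 |
| Serum biomarkers including IgG | 86, 94, 104 | 138, 146, 156 |
| Separate serum albumin | 90 | 142 |
| Serum and urine heparan sulphate (HS) | 86, 90, 94, 104 | 138, 142, 146, 156 |

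**Step 3: size.**
- Unpaired post-baseline visits: 2/12 = 17%.
- Paired visits including Day 0: 11/13 = 85%.
- With 5 subjects, up to 2 × 5 = 10 CSF samples are affected.

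**Step 4: distance to the nearest plasma.** 90 − 86 = 94 − 90 = 4 weeks, and 142 − 138 = 146 − 142 = 4 weeks, so 28 days nominally. With ±5 days on each visit the range is 28 ± 10 = 18 to 38 days. If the infusion in between is given, the 10-day minimum between infusions raises the lower end to 20 days.

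**Step 5: can anything else supply the missing value?** Section 5.2.1 allows remaining blood to be used for additional biomarkers.
- *Amino acids:* the blood scheduled at Weeks 90 and 142 is serum (albumin, HS), whereas Table 1 specifies plasma. Coagulation, the other plasma test, is not scheduled at these visits either. Nothing fills the gap.
- *IgG:* serum is being drawn, and Section 5.2.1 asks for serum IgG with the CSF. The value is called for in the text and may be obtainable, but the schedule and its footnotes do not tell the site to collect it.

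**Step 6: effect of moving a draw on the blood series.** Visits 78, 86, 94, 104 have gaps of 8, 8 and 10 weeks. Moving 86 to 90 gives gaps of 12, 4 and 10; moving 94 to 90 gives 8, 4 and 14. Weeks 130, 138, 146, 156 behave identically.

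**Step 7: blood limits.** Section 5.2.1 caps study blood loss at 1% of total volume in a single draw and 3% over 4 weeks, with total volume put at 80 to 90 mL/kg. That is 0.8 to 0.9 mL/kg per draw and 2.4 to 2.7 mL/kg over 4 weeks. The documents do not give tube volumes, so compliance after a move cannot be verified here.

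**The case against.** The strongest reply is that the pattern may be deliberate. At exactly these two visits the schedule adds serum albumin and an extra HS sample. Serum HS is Tier 1, while plasma amino acids and serum IgG are individually Tier 2 and are collected only if blood volume allows. The documents give no rationale, so neither oversight nor intent is established. The tier argument also works less well for IgG, because the index itself is Tier 1.

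Second, Section 3.4.3 asks only for a relation to plasma; it does not say same-visit. Pairing is put in words for albumin and IgG alone. That stands: for the amino acids, same-visit pairing is a sensible reading rather than a written rule that the schedule breaks.

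Third, a reader might infer that the IgG index cannot be derived at Weeks 90 and 142. The documents do not support this. Section 5.2.1 asks for serum IgG with the CSF sample, Table 1 makes the index Tier 1, and serum is drawn at both visits. The defect is a conflict between the text and the schedule with its albumin-only footnotes.

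Fourth, little rides on it. CSF-AI, a secondary endpoint, is paired at both visits. The CSF-only biomarkers are unaffected, and every MRI visit (Day 0, Weeks 24, 52, 104, 156) has paired blood. SAP Section 4 records that development was stopped on 11 July 2017, and SAP Sections 5.1.4.1 and 7.2.5 exclude exploratory analyses from the CSR. This sets the priority but does not remove the inconsistency.

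**Conclusion.** The point holds, at low priority. For the amino acids, 2 of 12 post-baseline CSF visits have no same-visit plasma value and no text supplies one; this rests on reading the endpoint as a same-visit comparison. For IgG, the schedule and its footnotes contradict Section 5.2.1 and the Tier 1 listing in Table 1 at the same two visits, so a site following the schedule alone would not draw the sample.

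Both measures are exploratory, 11 of 13 CSF visits are already paired, and no output planned in the SAP changes.

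**What to change.** In Appendix A, move (rather than add) the pre-dose plasma glutamic acid/glycine draw and the serum IgG/biomarker draw from Week 86 or 94 to Week 90, and from Week 138 or 146 to Week 142. All 13 CSF visits are then paired. Moving the earlier draw of each pair keeps the longest gap in the blood series at 12 weeks rather than 14. Add serum IgG to SOA footnote 8 and Table 1 footnote b so that they agree with Section 5.2.1.

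The cost is wording in the schedule and two footnotes, with no extra visit, puncture or total blood. It is not entirely free: the blood-only series becomes less evenly spaced, and somewhat more blood is taken at the puncture visit, within about 4 weeks of a neighbouring full panel. The 1% single-draw and 3% four-week limits must therefore be checked against actual tube volumes first. If they cannot be met, the protocol should state that the plasma comparison is not evaluated at Weeks 90 and 142. The SAP analyses need no change.
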